After passing an initial prescreening, potential participants will provide informed consent and be administered emailed, phone or videoconference-based screening assessments by trained research staff to assess the above inclusion and exclusion criteria. Participants who qualify after completing all screening assessments will then be sent or provided the study materials. This consists of study medication and self-monitoring equipment, including, as needed, a pregnancy test [for females of childbearing age not using contraception], oxygen saturation monitor, automated blood pressure monitor, and thermometer. We will finalize screening (ie confirming medical stability via oxygen saturation monitor, and vital sign measurement) prior to instructing participants to begin taking study medication, after which point (after taking first dose) they are considered "randomized", consistent with Intention to Treat principles.

Study Design

This study will randomize approximately n=152 participants. This study has an initial double-blind phase (to test the drug's effectiveness) followed by an open-label phase (to provide all participants with exposure to the drug, and allow a taper off of it for those initially taking active drug).

Assignment will be 1:1; (1) Active treatment: start and maintain fluvoxamine 100mg, three times daily. May reduce dose (or start at reduced dose) for tolerability reasons; (2) Control: placebo, three times daily. This drug vs placebo phase will last approximately 15 days and will be followed by an open-label fluvoxamine phase that will typically last 6-7 days but could last up to 15 days: 100mg two times daily for 3 days, then 50mg two times daily for 3 days, then discontinue.

Randomization will be stratified by age (we anticipate: 18-44, 45-54, 55-64 and ≥ 65 years, respectively, to reflect the age distribution of ascending risk for severe symptoms requiring hospitalization (https://www.cdc.gov/mmwr/volumes/69/wr/mm6912e2.htm#F2_down) and sex. Final determination of stratification will be made by the biostatistician ([name]). Stratified randomization schedules will be generated by statistician [name].

After the randomized phase, all participants will be followed for approximately 30 days to collect clinical data (i.e., on hospitalization and other clinical outcomes). Thus, total study participation is approximately 45 days (15 days randomized, 30 days follow-up).

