All enrolled participants will also be sent a longterm follow up survey which asks about persistent COVID 19 symptoms, and a PROMIS scale which asks about functioning and quality of life.

Management: To protect research staff, there will be no face-to-face contact with participants; all interactions will be fully-remote via Zoom videoconference and/or phone/text/email, as well as REDCap surveys pushed out to patients via their smartphones or other devices.

For consented participants who start protocolized treatment we will inform their relevant medical providers, such as a PCP, towards the goal of an informed and collaborative management strategy.

As this is a “prevention of clinical deterioration” study, it is anticipated that a minority (~10-15%) of participants will become hospitalized during the study, and that this will most likely occur during the randomized phase. Research staff under the physician investigators’ supervision will provide support including engagement with participants’ caregivers and physicians to ensure timely medical contact and emergency care (including calling 911).

If a study participant develops a decrease in oxygen saturation to less than 90% on room air on >2 readings, persistent increase in respiratory rate to >30 breaths per minute, persistent increase in Heart Rate to > 120 beats per minute, alteration in mentation, or severe worsening in shortness of breath, the research staff will direct them to seek emergency medical care at the nearest emergency department. If none of the above conditions are met, but the research staff still feel that the participant is unwell, one of the physician investigators will evaluate the participant via phone/telehealth and direct them for further care if needed. When a participant is directed to seek emergency medical care, they will be instructed to use a mask if available, and to identify themselves to EMS or to the Emergency Department staff as having been diagnosed with COVID-19.

Safety Assessments

We will assess for adverse events (including serious adverse events) daily via participant self-report during the first 15 days, and then again at the end of the study.

Outcome Assessments

As this is a prevention (of clinical deterioration) trial, the primary endpoint will be a “time to” clinical worsening analysis. Following the intention to treat principle, all participants who are confirmed to have taken at least one dose of study medication are included in the analyses.

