Definition of clinical worsening: Clinical worsening is defined meeting both of the following: (1) presence of dyspnea and/or hospitalization for shortness of breath or pneumonia, plus (2) decrease in O₂ saturation ($<92\%$) on room air and/or supplemental oxygen requirement in order to keep O₂ saturation $>92\%$. A laboratory-confirmed clinical endpoint is consistent with World Health Organization clinical trial recommendations (<https://www.who.int/blueprint/15-01-2020-nfr-bp-wg-clinical-trials-ncov.pdf?ua=1>).

Power analysis: The below table regards the primary endpoint. It assumes 80% power, alpha=0.05, and a 20% rate of progression to serious symptoms in the placebo group. The table shows sample size required based on reduction in that rate in the active (fluvoxamine) group. With total n=152 (76 per group), we would have 80% power to find a statistically significant difference in survival curves (i.e., time to clinical worsening) if the rate of progression with fluvoxamine is only 5% (i.e., a three-quarters reduction in the risk of clinical deterioration). This power calculation is conservative because it does not take into account the potentially improved power gained by stratification, or the enhanced power for Kaplan Meier vs. simple rates; therefore, we are likely to be sufficiently powered for a more modest treatment effect.

Treatment Response	N (each group)
.05	76
.06	90
.07	108
.08	131
.09	160
.10	199

We will also examine the following secondary endpoints:

1. clinical deterioration on a Likert-type scale: (1) moderate severity of illness as defined by O2 saturation <92% but no supplemental oxygen requirement; (2) O2 saturation plus supplemental oxygen requirement; (3) O2 saturation <92% plus hospitalization (related to dyspnea/hypoxia); (4) the above, plus ventilator support requirement; (5) the above, plus ventilator support for at least 3 days; (6) death.

2. clinical deterioration measured by number of days: (1) requiring supplemental oxygen; (2) requiring hospitalization; (3) requiring ventilator support.

These Likert-type assessments are based on our review of current COVID-19 treatment studies.

They will be collected in retrospect via patient or family report and/or medical records.

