3. Total symptomatic severity during the 15 days using a continuous scale of each patient's presenting symptoms on a 0-10 Likert scale (0= symptom not present, 10= symptom is very severe). Outcomes will be collected daily, with symptomatic data collected approximately twice daily via the technique of Ecological Momentary Assessment (ie "how bad is your symptom right now?"). The most severe symptom at baseline will be the focus. This data collection and analytic technique (with frequent measurement of the symptom[s] most relevant to the individual patient) should greatly increase precision and power (<https://www.ncbi.nlm.nih.gov/pmc/articles/PMC6524455/>).

Data management and analysis: Data will be collected in REDCap and outcomes will be collected by blinded research staff. The study statistician, [name], will conduct blinded (ie "treatment 1 vs treatment 2") analysis under the supervision of [name]. We may conduct an interim "futility" analysis at approximately n=100 participants. The primary analysis will be survival analysis of the primary outcome (clinical worsening), while secondary endpoints (symptomatic severity) will be examined using appropriate (descriptive, Area Under the Curve (AUC), and trajectory) comparisons.

Sharing of de-identified data from this study will be critical because it will help characterize this patient population and, if positive results, would immediately lead to a potential new treatment for COVID-19. Therefore it is planned that a pre-print of the article along with de-identified data will be posted on a public repository such as arxiv (arxiv.org). This has been standard during the pandemic in order to share results as rapidly as possible.

Additional measurements:

Baseline: vital signs (pulse, blood pressure, temperature), O2 saturation, weight and height, symptoms and symptomatic severity.

Follow-up: daily vital signs, O2 saturation, adverse events (participant self-report).

Risks

Potential risks associated with study assessments

There are no risks associated with any of the assessments.

Potential risks associated with study medication

Fluvoxamine:

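### Secondary endpoint 2 counts days of support with no death rule and no counting window, so early deaths shorten the count and can make the arm with more deaths look better

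*Combined protocol and SAP*

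**What the plan says.** In the Outcome Assessments section, the second of three secondary endpoints is "clinical deterioration measured by number of days: (1) requiring supplemental oxygen; (2) requiring hospitalization; (3) requiring ventilator support". Neither this section nor any other says how a participant who dies is scored. There is no worst rank, no assignment of the days after death, no form that combines survival with freedom from support, and no competing-risk method.

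The counting period is not given either. The Study Design section says that "total study participation is approximately 45 days (15 days randomized, 30 days follow-up", and the symptom endpoint is tied to the first 15 days, but endpoint 2 is tied to neither period.

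Death is an efficacy outcome only in secondary endpoint 1, an ordinal scale whose worst levels read "5) the above, plus ventilator support for at least 3 days; (6) death". The one analysis sentence that covers the secondary endpoints, under Data management and analysis, says "secondary endpoints (symptomatic severity) will be examined using appropriate (descriptive, Area Under the Curve (AUC), and trajectory) comparisons". It names symptom severity and nothing specific to day counts. On the analysis set, the plan says "all participants who are confirmed to have taken at least one dose of study medication are included in the analyses". Participants who die therefore stay in the comparison and need a score.

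**The concern.** Endpoints 1 and 2 are both presented as measures of clinical deterioration, and on endpoint 2 fewer days means less of it. Take a participant who dies after 2 ventilator days and a survivor ventilated for 12 days. Endpoint 1 places the first at level 6 and the second at level 5. Endpoint 2, read as written, gives the first 2 days and the second 12. A participant who dies before receiving any support scores 0, the same as one who never worsened.

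The Management section expects that "a minority (~10-15%) of participants will become hospitalized during the study". That is 152 × 0.10 = 15.2 to 152 × 0.15 = 22.8 participants, or about 15 to 23 non-zero hospital counts in the whole trial. With so few, two or three early deaths can change the comparison. Without a stated rule, the handling of deaths would have to be settled once outcomes are known.

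**Working it through.** **The plan's own figure.** The plan gives no number for endpoint 2, so only the sample size for the primary endpoint can be reproduced. Of the power table, the plan says "It assumes 80% power, alpha=0.05, and a 20% rate of progression to serious symptoms in the placebo group". The active rate is 5% and there are 76 per group. The formula for two proportions with pooled variance, two-sided 0.05 and no continuity correction is

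n = [1.960 × √(2 × 0.125 × 0.875) + 0.842 × √(0.20 × 0.80 + 0.05 × 0.95)]² / 0.15² = 75.1, rounded up to 76.

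This matches the plan, and the other five rows of the table reproduce as well. Nothing below changes that figure.

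**Inputs for the illustration.**
- From the documents: 76 per arm, hospitalisation h = 15% (upper end of the forecast), follow-up F = 45 days.
- Assumed, because the documents are silent: survivor stay L = 10 days, death after d = 2 hospital days, mortality among those admitted c = 10% in one arm and 30% in the other, and the same h in both arms.

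**Raw hospital days per participant**, h × [(1 − c) × L + c × d]:
- lower-mortality arm: 0.15 × (0.9 × 10 + 0.1 × 2) = 1.38
- higher-mortality arm: 0.15 × (0.7 × 10 + 0.3 × 2) = 1.14

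The arm with more deaths looks better by 0.24 day.

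**Days alive and out of hospital over 45 days, with any death scored 0**, (1 − h) × F + h × (1 − c) × (F − L):
- lower-mortality arm: 0.85 × 45 + 0.15 × 0.9 × 35 = 42.98
- higher-mortality arm: 0.85 × 45 + 0.15 × 0.7 × 35 = 41.93

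The arm with more deaths is now worse by 1.05 days.

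**When the direction is wrong.** With equal h, the difference in raw days is h × (difference in c) × (d − L). Its sign depends only on whether death comes before survivors' discharge. With 11 admissions per arm (15% of 76 is 11.4) and 1 against 3 deaths, total hospital days are:

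| Survivor stay | Death at day 1 | Day 2 | Day 4 |
|---|---|---|---|
| 7 days | 71 vs 59 | 72 vs 62 | 74 vs 68 |
| 10 days | 101 vs 83 | 102 vs 86 | 104 vs 92 |
| 14 days | 141 vs 115 | 142 vs 118 | 144 vs 124 |

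The arm with more deaths has fewer days in every cell. If death comes after 20 days and survivors stay 10, the totals are 120 vs 140 and the count points the right way.

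**How often.** In 100,000 simulated trials with the first set of assumptions, the raw count favoured the higher-mortality arm in 67%, against 21% for days alive and out of hospital. With 10% hospitalised, the figures were 63% and 25%.

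**Understating a benefit.** Use the planned primary events as a stand-in for admissions: 0.20 × 76 ≈ 15 on placebo and 0.05 × 76 ≈ 4 on fluvoxamine, each with 10 days. The means are 150/76 = 1.97 and 40/76 = 0.53, a gap of 1.45. If 3 of the 15 placebo patients die after 2 days, the placebo mean is (12 × 10 + 3 × 2)/76 = 1.66 and the gap is 1.13.

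**The case against.** The plan is silent on death; it does not assign death a favourable score. A reader might infer that endpoint 2 treats death as a good outcome. That goes too far: a death after 2 ventilator days still counts as worse than the large majority of participants, who score 0. Only a death before any support scores like an uneventful course.

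A reader might also infer that endpoints 1 and 2 always rank patients in opposite orders. They do so only when the death comes before the other patient's discharge or weaning.

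A third tempting reading is that the count would reverse the effect the trial hopes to find. Under the planned 15 against 4 events it would not. With k placebo deaths at day 2, the placebo total is 150 − 8k, and it falls below 40 only when k reaches 14 of the 15. That example shows attenuation. It also treats primary events as admissions, although the primary endpoint can be met without one. The reversal shown above needs similar hospitalisation in the two arms and a clear difference in mortality, and the documents support neither.

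There is mitigation too. Endpoint 1 ranks death worst and serious adverse events are collected, so an excess of deaths would be visible elsewhere. The plan attaches no hierarchy or success claim to endpoint 2.

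These points limit the size of the problem but do not remove it. No section supplies a death rule or a window, every dosed participant is analysed, and endpoint 2 would be reported as a result in its own right.

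**Conclusion.** The concern holds in a limited form. Endpoint 2 has no death rule and no counting window, so deaths that come before other patients' discharge shorten the count. That can understate a real benefit and, when hospitalisation is similar in the two arms, can favour the arm with more deaths. The reversal (1.38 against 1.14 raw days, compared with 42.98 against 41.93 days alive and out of hospital) rests on assumed mortality, length of stay and time of death. It is an illustration and not an estimate. With late deaths the raw count points the right way. Few deaths are likely, the endpoint is secondary, and the primary analysis and the 76 per group stand.

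**What to change.** Define endpoint 2 as days alive and free of (1) supplemental oxygen, (2) hospital and (3) ventilator support, counted from the first dose over the full follow-up of about 45 days, with the last day fixed in the plan. Score any death in that window 0, or give it the worst rank. Compare the arms by a rank test, since most participants will tie at the maximum. Report deaths and the raw day counts by arm beside it.

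The window should not stop at the end of the randomised phase. A participant ventilated on Day 14 who died on Day 17 would then score about 13 ventilator-free days out of 15, nearly the best result. The longer window takes in the open-label phase, when placebo participants also receive fluvoxamine. The plan expects most admissions before then, so the dilution should be small.

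The cost is a redefined secondary endpoint. It needs the fact of death, which endpoint 1 already requires, and enough of a date to place it in the window. The support days are collected anyway. The primary analysis and sample size do not change.

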Recruitment & retention: For the present study, participants will be recruited through EPIC, physician referrers, doctor’s hotlines, COVID-19 Testing Centers, and Emergency Rooms (microbiology lab). They may also be recruited, as needed, via word of mouth, referrals by colleagues, the Healthy Mind Lab website (www.healthymind.wustl.edu), flyers, and email notification. Participants will be considered eligible per the inclusion/exclusion criteria and at the PI’s determination. Both genders will be enrolled without regard to race, ethnicity, or religion. Potential participants undergo screens by email and phone/videoconference.

The proposed study will require voluntary participation of individual persons and will abide by all federal regulations related to human subject protection, inclusion of women and minorities, and privacy of individually identifiable health information. As with any study that collects sensitive information, breach of confidentiality is a potential risk. To mitigate this risk, all study personnel will undergo training specific to the use of human participants in research (CITI), will be Health Insurance Portability and Accountability Act (HIPAA) and Good Clinical Practices (GCP) trained, and will be approved by the Washington University in St. Louis Institutional Review Board (IRB). Throughout the study, we will confirm plans to assure: 1) accurate, complete, and verifiable data collection and 2) the rights and well-being of human subjects will be protected, in accordance with 45 CFR 46 (Protection of Human Subjects) and, as applicable, 21 CFR part 50 (Protection of Human Subjects). Additionally, all data will be maintained strictly according to the HIPAA “two lock” policy. Only study personnel will have access to this data.

Participation in the proposed study-supported activities will be entirely voluntary and permitted only following completion of all consent-related procedures. We view informed consent as an ongoing process, and will continue the informed consent conversation with subjects throughout their participation.

Inclusion and Exclusion Criteria

Inclusion criteria:

- 1) men and woman age 18 and older;
- 2) Outpatients (living in the community)
- 3) Proven SARS-CoV-2 positive (per lab or physician report).
- 4) Currently symptomatic with one or more of one or more of the following symptoms: fever, cough, myalgia, mild dyspnea, diarrhea, vomiting, anosmia (inability to smell), ageusia (inability to taste), sore throat.

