General comments: Fluvoxamine is an antidepressant drug that functions as a selective serotonin reuptake inhibitor (e.g., similar to escitalopram (Lexapro), fluoxetine (Prozac), sertraline (Zoloft), etc – among the most commonly prescribed drugs in the US). Its risk profile below is for chronic use in a psychiatrically ill population; the risks for short-term use in a non-psychiatric population are likely lower. The research team will carefully evaluate co-prescribed drugs as well as OTC medications and caffeine use, to mitigate drug-drug interactions. We anticipate approximately 20% of participants will be on current SSRI/SNRI use at recruitment – will include these individuals, so long as the participant can be safely switched over to fluvoxamine briefly.

Likely risks: none.

Less likely (1-10%): Nausea, Vomiting, Weight loss, Yawning, Loss of appetite, Agitation/Nervousness/Anxiety, Insomnia, Somnolence, Tremor, Headache, Dizziness, Palpitations, Tachycardia (high heart rate), Abdominal pain, Dyspepsia (indigestion), Diarrhea, Constipation, Hyperhidrosis (excess sweating), Asthenia (weakness), Malaise, Sexual dysfunction (including delayed ejaculation, erectile dysfunction, decreased libido, etc.), Xerostomia (dry mouth).

Rare (<1%): Arthralgia, Hallucination, Confusional state Extrapyrmidal side effects (e.g. dystonia, parkinsonism, tremor, etc.), Orthostatic hypotension, Cutaneous hypersensitivity reactions (e.g. oedema [buildup of fluid in the tissues], rash, pruritus), Mania (elevated mood together with reduced need for sleep and increased energy), seizures, Abnormal hepatic (liver) function, Photosensitivity (being abnormally sensitive to light), Galactorrhoea (expulsion of breast milk unrelated to pregnancy or breastfeeding).

Potential risk associated with Breach of Confidentiality:

One risk of participating in this study is that confidential information may be accidentally disclosed. We will use our best efforts to keep the information about participants secure. All private information is stored in secured areas and on encrypted and password-protected servers.

Other risks:

There may also be unknown risks. We will adjust the informed consent process if new risks are identified.

Adequacy of Protection Against Risks

Recruitment and Informed Consent

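### Symptom endpoint 3 tracks a different kind of symptom in different participants, and the AUC and trajectory comparisons specify no adjustment for which one it is

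*Combined protocol and SAP*

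**What the plan says.** Under Outcome Assessments, secondary endpoint 3 is "Total symptomatic severity during the 15 days using a continuous scale", scored 0 to 10 and collected about twice daily. The plan adds "The most severe symptom at baseline will be the focus" and expects that this individualised, frequent measurement "should greatly increase precision and power".

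Inclusion criterion 4 requires at least one of "fever, cough, myalgia, mild dyspnea, diarrhea, vomiting, anosmia (inability to smell), ageusia (inability to taste), sore throat".

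Under Data management and analysis, the whole analysis of this endpoint is that "secondary endpoints (symptomatic severity) will be examined using appropriate (descriptive, Area Under the Curve (AUC), and trajectory) comparisons". No model, covariate or symptom term is named. Under Study Design, randomisation is stratified by age and sex, not by symptom.

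Under Additional measurements, the baseline data include "O2 saturation, weight and height, symptoms and symptomatic severity".

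In the section on potential risks of the study medication, the list that begins "Less likely (1-10%): Nausea, Vomiting, Weight loss" also contains diarrhea. Two of the nine entry symptoms are therefore listed drug effects as well.

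**The concern.** When the focus is each participant's own worst symptom, a 15-day AUC is a fever AUC in one participant and a smell AUC in another. If these symptoms run different courses whatever the treatment, the difference between symptom types becomes between-participant variance in the arm comparison. A baseline covariate can remove that part. Which symptom is tracked is fixed before the first dose and already recorded, so the covariate needs no new data.

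An analyst would not necessarily add this term by default. Baseline score, age and sex are the usual candidates. A covariate chosen after the data are seen carries less weight than one written down beforehand. At stake is the precision and interpretability of one secondary endpoint, which the plan designed with precision in mind.

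**Working it through.** **The plan's own figure.** The only sample size in the plan is for the primary endpoint. For 20% against 5%, two-sided alpha 0.05, 80% power and pooled variance without continuity correction:

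n = [1.960·√(2·0.125·0.875) + 0.842·√(0.20·0.80 + 0.05·0.95)]² / 0.15² = (0.917 + 0.383)² / 0.0225 ≈ 75.1, so 76 per arm.

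The other five rows of the power table reproduce as well. None of this bears on endpoint 3, for which the plan gives no SD, effect size or power.

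**Inputs for endpoint 3.**
- From the documents: 152 participants, 76 per arm, 1:1 allocation.
- Assumed: a share f of 15% or 25% is tracked on loss of smell or taste. Their 15-day AUC differs from the others by d = 15, 30 or 45 points (1, 2 or 3 points per day). The SD within groups is 30.
- Also assumed: a two-sided test, no dropout, roughly normal AUC and a common treatment effect across symptoms.

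**Share of variance explained.** R² = f(1−f)d² / [f(1−f)d² + 30²]. For f = 0.15 and d = 15: 0.1275 × 225 = 28.7, and 28.7 / 928.7 = 0.031.

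**Cost of adjusting.** Four symptom groups need three terms. The variance is multiplied by (152−3)/(152−3−3) = 149/146 = 1.021. Break-even is R² = 1 − 146/149 = 2.0%.

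**Net result.** Variance ratio V = (1−R²) × 1.021. The standard error changes by √V − 1, and the equivalent total is 152/V. Power is taken at the difference that gives 80% unadjusted, (1.960 + 0.842)·√(2/76) = 0.454 SD.

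| f | d | R² | V | SE change | Equivalent N | Power |
|---|---|---|---|---|---|---|
| 0.15 | 15 | 3.1% | 0.989 | −0.6% | 154 | 80.4% |
| 0.25 | 15 | 4.5% | 0.975 | −1.3% | 156 | 81.0% |
| 0.15 | 30 | 11.3% | 0.905 | −4.9% | 168 | 83.8% |
| 0.25 | 30 | 15.8% | 0.859 | −7.3% | 177 | 85.6% |
| 0.25 | 45 | 29.7% | 0.718 | −15.3% | 212 | 91.1% |

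**Below the range.** With d = 7.5 and f = 0.15, R² is about 0.8% and V = 1.012, so adjustment loses slightly. With R² = 0, V = 1.021 and power is 79.2%.

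**Finer adjustment.** Keeping all nine symptoms separate needs eight terms: 149/141 = 1.057, break-even R² about 5.4%, and power 77.8% if symptom type explains nothing. Grouping is the cheaper choice.

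**Bias.** In simulations with nine symptoms (4,000 trials per setting, equal and skewed frequencies), the bias in the arm difference was at most 0.007 SD with or without adjustment. At R² of 10%, 20%, 30% and 40%, the variance ratios with eight terms were 0.96–0.98, 0.84–0.85, 0.73–0.75 and 0.60–0.62, in line with the formula.

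**The case against.** The strongest reply is that the plan is silent and has made no choice against adjustment. The comparisons it calls appropriate neither include nor exclude a symptom term, and age, sex and baseline severity are equally unmentioned. That stands. A reader might infer that the plan ignores symptom type and so throws precision away for nothing. The documents do not support this: no unadjusted model is stated, the loss depends on assumed values, and adjustment has a cost that exceeds its benefit below an R² of about 2%.

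Other objections also stand in part:
- **The scored variable is not settled.** The endpoint's title speaks of total severity, and its definition of presenting symptoms in the plural. The worst symptom is the focus, but is not said to be the only symptom scored. The point applies to the worst-symptom score.
- **Baseline severity may already predict AUC.** The figures compare adjustment for symptom with no adjustment. The further gain over a model with baseline severity cannot be computed from the documents.
- **Chance imbalance in symptom mix is not a separate harm.** If 20% are tracked on smell or taste, the between-arm difference in that share has an SD of √(2·0.2·0.8/76) = 6.5 percentage points. That variation is already in the standard error.
- **The gastrointestinal overlap is a modest point.** A main-effect covariate cannot reveal an opposite effect in participants tracked on diarrhea or vomiting. Only a by-group description could, in a subgroup of unknown size. Adverse events are collected daily in any case.

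What the objections do not remove is that the tracked symptom can differ between participants, the covariate is already recorded, and the plan does not say whether it will be used.

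**Conclusion.** The point holds as a low-cost improvement to a secondary endpoint. No adjustment for the tracked symptom is specified. Adjusting would help if symptom type explains more than about 2% of AUC variance, which is plausible for symptoms as unlike as fever and loss of smell but is not shown by any figure in the documents.

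The gain runs from negligible to worthwhile: a standard error lower by about 0.6% to 15%, or 154 to 212 equivalent participants. It rests wholly on the assumed shares, AUC gaps and SD. The calculation is for the AUC; no size is offered for the trajectory model.

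It would be wrong to read this as a flaw in validity. Randomisation keeps the arm comparison unbiased with or without the covariate, and the primary endpoint and sample size are untouched.

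**What to change.** In Data management and analysis, pre-specify that:
- the worst-symptom AUC is compared by a linear model, and the trajectory by its longitudinal model, each adjusted for baseline severity of the tracked symptom and for tracked-symptom group;
- the groups are, for example, respiratory/throat (cough, mild dyspnea, sore throat), fever/myalgia, gastrointestinal (diarrhea, vomiting) and smell/taste, with sparse groups merged before unblinding;
- the trajectory model includes group-by-time;
- arm differences by group are reported descriptively.

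The same text should say whether the scored variable is the worst symptom or a total, and how ties for worst are resolved, because the covariate depends on both.

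The cost is a few lines of text and no new data. In the AUC model, symptom group uses three degrees of freedom, and power falls from 80% to 79.2% if it explains nothing. Baseline severity uses one more: if neither explained anything, the factor would be 149/145 = 1.028 and power about 78.9%. The group-by-time terms add parameters to the trajectory model that are not costed here.
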